6.8.1.3 Dose modifications due to other savolitinib-related toxicity

Table 9 Dose modifications for savolitinib-related toxicities

NCI CTCAE toxicity grade	Action
Grade 0, 1, or 2	None
Grade 3^a	Hold savolitinib and follow the algorithm below:

 • Grade 3 toxicity for ≤ 7 days and resolves to \leqGrade 2 or baseline within 14 days of onset • Toxicity persists at Grade 3 for >7 days 	
 • Resume dosing at same dose or one reduced dose level (maximum of 2 dose reductions) as clinically appropriate • Discontinue savolitinib
Grade 4	Follow the algorithm below:

 • Expected to be manageable/reversible with dose reduction • Not expected to be manageable/reversible with dose reduction 	
 • Hold dosing and consult with AstraZeneca study physician • Discontinue savolitinib
Recurrence of Grade 3	

 • Grade 3 toxicity for ≤ 7 days and resolves to \leqGrade 2 or baseline within 14 days of onset • Grade 3 toxicity for >7 days 	
 • Resume dosing at same dose or one reduced dose level (maximum of 2 dose reductions) as clinically appropriate • Discontinue savolitinib
Recurrence of Grade 4	
 • Discontinue savolitinib

No more than 2 dose reductions will be allowed for any patient. Patients on 400 mg savolitinib due to weight <50 kg will only be allowed one dose reduction. Patients requiring additional dose modifications due to toxicity will discontinue study treatment.

^a Despite appropriate supportive care

6.8.1.4 Dose modifications for savolitinib-related QTcF prolongation

Dose modifications for savolitinib-related QTcF prolongation are reported in Table 10

Table 10 Dose modifications for savolitinib-related QTcF prolongation

NCI CTCAE toxicity grade	Action
Grade 0, 1, or 2	None
Grade 3	Hold dosing and follow algorithm below

 Patients with QTcF prolongation to >500 msec on at least two separate ECGs If the toxicity does not resolve to QTcF <481msec within 21 days 	
 Consult with a cardiologist to validate ECG finding. Ensure cardiac surveillance and take actions in accordance with clinical standard. Regular ECGs performed until resolution to QTcF <481 msec and then restart drug at one reduced dose level Discontinue study drug and consult with a cardiologist for further management as clinically indicated
Grade 4	

 QTcF \geq501 or >60 msec change from baseline and Torsades de pointes or polymorphic ventricular tachycardia or signs/symptoms of serious arrhythmia 	
 Discontinue study drug and consult with a cardiologist for further management as clinically indicated

6.8.1.5 Risk minimisation activities for identified and potential risks associated with savolitinib

The following section highlights risk minimisation activities for the key identified and potential risks identified in either preclinical studies or from ongoing clinical studies.

Identified risks

Liver Function Tests

Drug-induced liver injury (DILI) is an AESI for savolitinib and requires specific monitoring. For more information see Section 6.1.1 or the most current version of the IB. Weekly monitoring of liver function tests will be done for the first 9 weeks and then at the start of every cycle thereafter. The hepatotoxicity management algorithm (Section 6.8.1.2) now clearly defines and limits the patients on savolitinib who can be re-challenged to those with lower grade abnormalities with rapid resolution. As stated in the eligibility criteria and risk mitigation sections, patients with significantly abnormal baseline liver function tests will be excluded from the study. In addition, as mentioned in Section 6.1.1, a 400-mg dose for patients below 50 kg will be used to potentially reduce the risk of hepatotoxicity.

Pyrexia and hypersensitivity

Pyrexia and hypersensitivity have been identified as a risk for patients receiving savolitinib. Pyrexia was followed in some cases by DILI (see above) or an association of symptoms

suggestive of hypersensitivity such as, but not limited to, allergic rash, cytopenias, myalgia/arthritis [REDACTED]. Patients who experience pyrexia with or without an association of the above symptoms after initiation of savolitinib treatment must follow the toxicity management guidelines.

QTc prolongation

QTc interval prolongation potential of savolitinib 600mg was assessed in a thorough QT study in healthy volunteers. Analysis of the data concluded that it is a positive study as the upper two-sided 90% CI for the mean $\Delta\Delta\text{QTcF}$ was 13.6 and 14.0 msec at 4 and 5 hours, respectively. Regular ECG assessments will be done throughout the study according to the study plan. Patients who present ECG abnormalities with or without symptoms during treatment with savolitinib must follow the QTc prolongation toxicity management guidelines.

Oedema

Peripheral oedema has been observed in patients receiving savolitinib. These events have been Grade 1 or 2, and the incidence does not appear to be dose related. Oedema has also been observed with other MET inhibitors including onartuzumab and crizotinib. Oedema should be monitored by clinical examination and measurement of weight. Diuretic therapy should be considered at the discretion of the investigator. Renal function will be carefully monitored.

Nausea/vomiting

Nausea and/or vomiting are common causally related AEs seen in clinical trials of savolitinib. If vomiting occurs after taking savolitinib, the patient should be instructed not to retake the dose. Patients should take the next scheduled dose of savolitinib. Patient reports of nausea and vomiting are expected to be evaluated and treated by investigators according to local practice (eg, use of antiemetic therapy, intravenous fluid replacement).

Fatigue

Fatigue is one of the more common causally related AEs seen in clinical trials of savolitinib. Follow the general guidance in the protocol for dose interruptions/reductions/ discontinuations as per Section 6.8.1.

Potential risks

Phototoxicity and/or rash

Results of an in vitro (3T3) test suggest the potential for phototoxicity. Measures to prevent photosensitivity have been included in ongoing studies. There have been no reported cases of photosensitive rash. Adverse events of Grade 1 rash, erythema and pruritus have been reported in some patients. During savolitinib therapy and for 4 weeks after the last dose, patients should be advised to avoid prolonged exposure to sun, wear protective clothing and a

hat and seek shade from the sun as far as possible; in addition, an SPF30+ sunscreen should be used. Exposure to other sources of UV light including sunbeds, tanning booths, etc. should be avoided. If sunburn occurs, it is important to discontinue the study medication and take action under the direction of a doctor. Keeping the area of skin eruption moist and applying wet dressings may help relieve the symptoms. Reactions may last a few days, however severe reactions may last up to a few weeks. Topical steroid creams may be helpful in treating the redness, and antihistamines are generally helpful in minimizing the itching. In severe cases, a short course (10-14 days) of oral steroids, under the direction of a doctor, can be used.

Testicular toxicity

In the 3-month GLP dog study, histopathological findings were seen in the testes (seminiferous tubular degeneration) and/or epididymides (cellular debris, reduced cellularity/sperm) at all doses levels. Group mean exposures in male dogs at the lowest observed effect level (LOEL) were approximately 4-fold above the group mean AUC in patients at the 600 mg QD dose (17.06 µg/mL). A no observed effect level (NOEL) was not identified for the testicular/epididymal findings. Reversibility was not assessed in this study, but lesions of this nature and severity (minimal to mild) would be expected to recover given sufficient time off-dose.

Male patients taking savolitinib must use a condom during sexual intercourse with a female partner of childbearing potential (pregnant or not) and refrain from donating sperm during the study and for 6 months after their last dose.

6.8.2 Management of sunitinib-related toxicities

Table 11 Dose modifications for sunitinib-related toxicities (including hepatic)

NCI CTCAE toxicity grade	Action
Grade 0, 1, or 2	None
Grade 3^a	Hold sunitinib and follow the algorithm below:

 Toxicity at Grade 3 for ≤7 days and resolves to ≤Grade 1 or baseline Toxicity persists at Grade 3 for >7 days 	
 Resume dosing at one reduced dose level (maximum of 2 dose reductions) Discontinue sunitinib
Grade 4	Follow the algorithm below:

 Expected to be manageable/reversible with dose reduction Not expected to be manageable/reversible with dose reduction 	
 Hold dosing and consult with AstraZeneca study physician Discontinue sunitinib
Recurrence of Grade 3	

 Grade 3 toxicity for ≤7 days and resolves to ≤Grade 1 or baseline Grade 3 toxicity for >7 days 	
 Resume dosing at one reduced dose level (maximum of 2 dose reductions) Discontinue sunitinib
Recurrence of Grade 4	
 Discontinue sunitinib

No more than 2 dose reductions will be allowed for any patient. Patients on 400 mg savolitinib due to weight <50 kg will only be allowed one dose reduction. Patients requiring additional dose modifications due to toxicity will discontinue study treatment.

^a Despite appropriate supportive care

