be performed. The ePRO device and all unused study medication and study medication bottles should be returned.
- 19 A safety follow-up will be performed 30 (± 7) days after discontinuation of study medication, to follow-up on any SAE/AE's and record any subsequent
cancer therapy. If there are no ongoing SAE/AEs at the time of drug discontinuation, the safety follow-up can be done via telephone contact.
- 20 All subsequent anti-cancer therapies and OS status will be documented at least every 12 weeks until death, loss to follow-up, withdrawal of consent, or end
of study, whichever comes first.
- 21 Blood liver functions (AST, ALT, alkaline phosphatase and total bilirubin) will be monitored weekly x 9 and then at the start of each cycle. In some
situations, blood for LFTs may be drawn at a local lab on the days when there is no scheduled clinic visit although the results must be faxed to the treating
institution immediately so they can be evaluated in light of the hepatotoxicity algorithm (Section 6.8.1.2 for savolitinib and Section 6.8.2 for sunitinib) and
entered into the database.
- 22 An IVRS/IWRS transaction needs to be done at every dispensing visit at the start of each cycle. Additionally, every dose reduction needs to be recorded in
IVRS/IWRS.
- 23 Please see section 6.3. From the part 1 screening visit until the part 2 screening visit, only SAEs related to study procedures must be reported (AEs do not
require reporting). From the main study screening (Part 2) onwards, all AEs/SAEs must be reported
- 24 Smoking status (Yes (current smoker) /No (not currently smoking)) will be recorded at the time of the main study screening (Part 2) visit.
- 25 Body weight will be assessed every cycle, and more frequently if clinically indicated. The dose of savolitinib will not change for patients who started the
study at < 50 kg (ie, 400 mg), even if their weight increases to ≥ 50 kg during the course of the study.
- 26 20 mL for [REDACTED] at the Part 1 screening visit only (see Section 5.7.4)
- 27 Only necessary if there are ongoing toxicities
- 28 A tumour biopsy after treatment discontinuation should be strongly encouraged regardless of treatment arm, particularly for patients who had responded to
treatment. See section 5.7.7.
- 29 See Table 2 (Section 5.2.1) for list of chemistry evaluations
- 30 Hepatitis serology includes HBsAg, anti-HBc (qualitative), HBV DNA, HCV antibody, HCV RNA (if HCV antibody is positive)

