5.2 Safety assessments

5.2.1 Laboratory safety assessments

Blood and urine samples for determination of clinical chemistry, haematology, and urinalysis will be taken at the times indicated in the Study Plan (see Table 1).

The following safety laboratory variables will be measured:

Table 2 Standard Laboratory Safety Assessment Panel

Clinical chemistry safety	Haematology
S/P-Albumin	B-Absolute leucocyte differential count
S/P-Alkaline phosphatase ²	B-Eosinophils
S/P-ALT ²	B-Haemoglobin
S/P-Amylase	B-Leucocyte cell count
S/P-AST ²	B-Lymphocytes
S/P-Bilirubin, total ^{2,4}	B-Neutrophils
S/P-Calcium, total	B-Platelet count
S/P-Creatinine	Urinalysis
S/P-Free T4 ³	U-Dipstick-Blood
S/P-Glucose	U-Dipstick-Glucose
S/P-HBsAg ⁵ , anti-HBc (qualitative), HBV DNA ⁶ , HCV antibody, HCV RNA ⁷	U-Dipstick-Ketones
S/P-Lactate dehydrogenase ³	U-Dipstick- Leukocyte esterase or Leukocyte count
S/P-Magnesium	U-Dipstick-Protein ¹
S/P-Phosphate	
S/P-Potassium	
S/P-Sodium	
S/P-Thyroid Stimulating Hormone ³	
S/P-Total Protein	
S/P-Urea nitrogen	

- ¹ If 3+ or greater proteinuria is identified by dipstick assessment, a 24-hour urine collection for formal quantification of the level of protein excretion should be performed
- ² Designates tests that are considered liver function tests (LFTs) and are to be done weekly x 9 and then at the start of every course thereafter. Guidelines for management of hepatotoxicity are in section 6.8.1.2 for savolitinib and section 6.8.2 for sunitinib
- ³ Thyroid function studies and LDH are to be done at the main study (Part 2) screening visit, and at the start of every cycle thereafter
- ⁴ If total bilirubin is >2x ULN, then fractionate into indirect and direct bilirubin
- ⁵ If the HBsAg test is negative, the anti-HBc test should be still performed
- ⁶ HBV DNA test should be available for all patients that have had a previous HBV infection or are positive for HBsAg
- ⁷ HCV RNA qualitative test is only needed if the HCV Ab test is positive, and must be negative for the patient to be eligible.

Unscheduled blood or urine samples may need to be taken at the onset and as a part of a follow-up of some SAEs. The results should be added to the clinical trial database.

In case a patient shows an AST or ALT ≥ 3 x ULN and total bilirubin ≥ 2 x ULN please refer to Appendix E 'Actions Required in Cases of Increases in Liver Biochemistry and Evaluation of Hy's Law', for further instructions.

For blood volumes see Section 5.7.12

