6.3.3 Variables

The following variables will be collect for each AE;

- AE (verbatim).
- The date and time when the AE started and stopped.
- Worst CTCAE grade and changes in grade during the course of the AE.
- Whether the AE is serious or not.
- Investigator causality rating against the Investigational Product (IP) (yes or no).
- Action taken with regard to IP.
- AE resulted in patient's withdrawal from study (yes or no).
- Outcome.

In addition, the following variables will be collected for SAEs:

- Date AE met criteria for serious AE.
- Date Investigator became aware of serious AE.
- AE is serious due to (provide all seriousness criteria applicable).
- Date of hospitalisation (if applicable).
- Date of discharge (if applicable).
- Probable cause of death (if applicable).
- Date of death (if applicable).
- Autopsy performed (if applicable).
- Causality assessment in relation to Study procedure(s).
- Causality assessment to other medication.
- Description of AE.

It is important to distinguish between serious and severe AEs. Severity is a measure of intensity whereas seriousness is defined by the criteria in Section 6.2. An AE of severe intensity need not necessarily be considered serious. For example, nausea that persists for several hours may be considered severe nausea, but not a SAE unless it meets the criteria shown in Section 6.2. On the other hand, a stroke that results in only a limited degree of disability may be considered a mild stroke but would be a SAE when it satisfies the criteria shown in Section 6.2.

The grading scales found in the National Cancer Institute (NCI) CTCAE will be utilised for all events with an assigned CTCAE grading. For those events without assigned CTCAE grades

the recommendation is that the CTCAE criteria that convert mild, moderate and severe events into CTCAE grades should be used.

A copy of the CTCAE version can be downloaded from the Cancer Therapy Evaluation program website (<http://ctep.cancer.gov>).

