6.3.7 Hy's Law

Cases where a patient shows elevations in liver biochemistry may require further evaluation and occurrences of AST or ALT ≥ 3 xULN together with total bilirubin ≥ 2 xULN may need to be reported as SAEs. Please refer to Section 6.8.1.2 and Appendix E for further instruction on cases of increases in liver biochemistry and evaluation of Hy's Law.

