6.8.1.2 Dose modification due to savolitinib-related hepatotoxicity

- Promptly evaluate patients with elevated LFTs during study treatment for alternative aetiologies and potential Hy's law criteria (ALT or AST ≥ 3 x ULN **together with** TBL ≥ 2 xULN) and discontinue potential contributing concomitant medications or alternative causal agents, as well as anti-coagulants, if appropriate.

- Ensure a PK sample is collected as soon as feasible after the patient is diagnosed with abnormal LFTs necessitating drug interruption. The date and time that the PK sample was drawn and the date and time of the last savolitinib dose prior to the PK sample must be recorded in the eCRF.

If a patient discontinues due to an LFT abnormality, LFT monitoring should continue until resolution to grade 1 or baseline or an apparent plateau has been reached.

- 1 Discontinue savolitinib if
 - ALT or AST >8x ULN, or
 - ALT or AST >5x ULN for >2 weeks, or
 - ALT or AST >3x ULN and (TBL>2x ULN or INR>1.5 if not on anticoagulants that elevate the INR).
 - AST or ALT >3x ULN with the appearance of fatigue, nausea, vomiting, right upper quadrant pain or tenderness, fever, rash, and/or eosinophilia >5%
- 2 Withhold savolitinib if ALT or AST >5-8x ULN without TBL elevation above baseline or ULN, repeat LFT testing twice a week for 1 week;
 - If improved to grade 1 or baseline in 1 week, resume at reduced dose with LFT testing twice a week for 6 weeks;
 - If not, discontinue
- 3 Withhold savolitinib if ALT or AST >3x ULN and concurrent TBL 1.5~2x ULN, repeat LFT testing twice a week for 1 week,
 - If both ALT/AST and TBL improve to grade 1 or baseline in 1 week, resume at reduced dose with LFT testing twice a week for 6 weeks
 - If not, discontinue
- 4 Continue savolitinib if ALT or AST >3-5x ULN without TBL elevation above baseline or ULN, repeat LFT testing every week
 - If ALT or AST are trending upward, withhold dosing and repeat LFT twice a week for 1 week;
 - if improved to grade 1 or baseline in 1 week, resume at same dose with LFT testing every week for 6 weeks
 - if improved to grade 1 or baseline in 2 weeks, resume at reduced dose with LFT testing every week for 6 weeks
 - If not, discontinue
- 5 Discontinue savolitinib for recurrent Grade 3 ALT or AST (>5x ULN)
- 6 Discontinue savolitinib for recurrent Grade 2 ALT or AST (>3-5x ULN) and TBL >1.5~2x ULN

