6.8.2.1 Risk minimisation activities for risks associated with sunitinib

Adrenal function: Physicians prescribing SUTENT are advised to monitor for adrenal insufficiency in patients who experience stress such as surgery, trauma or severe infection.

Dermatologic: Severe cutaneous reactions have been reported with sunitinib, including cases of erythema multiforme (EM), Stevens-Johnson syndrome (SJS), and toxic epidermal necrolysis (TEN), some of which were fatal. If signs or symptoms of SJS, TEN, or EM (eg, progressive skin rash often with blisters or mucosal lesions) are present, sunitinib should be discontinued. If a diagnosis of SJS or TEN is suspected, sunitinib must not be re-started.

Hepatic: Sunitinib has been associated with hepatotoxicity, which may result in liver failure or death. Liver failure has been observed in clinical trials (7/2281 [0.3%]) and post-marketing experience. Liver failure signs include jaundice, elevated transaminases and/or hyperbilirubinemia in conjunction with encephalopathy, coagulopathy, and/or renal failure. Sunitinib should be interrupted for Grade 3 or 4 drug-related hepatic adverse events and discontinued if there is no resolution. Do not restart sunitinib if patients subsequently experience severe changes in liver function tests or have other signs and symptoms of liver failure.

Hypertension: Patients should be monitored for hypertension and treated as needed with standard anti-hypertensive therapy. Interruption and re-initiation at a reduced dose should be implemented as per Table 8. Grade 3 hypertension ($>160/100$, more intensive therapy than was previously used indicated) was observed in 50/375 treatment-naïve RCC patients (13%) on sunitinib. Severe hypertension (>200 mmHg systolic or 110 mmHg diastolic) occurred in 32/375 treatment-naïve RCC patients (9%) on sunitinib.

Hypoglycaemia: Sunitinib has been associated with symptomatic hypoglycemia, which may result in loss of consciousness, or require hospitalisation. Hypoglycemia has occurred in clinical trials in 2% of the patients treated with sunitinib for RCC. Reductions in blood glucose levels may be worse in diabetic patients. Check blood glucose levels regularly during and after discontinuation of treatment with sunitinib. Assess if anti-diabetic drug dosage needs to be adjusted to minimise the risk of hypoglycemia.

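### Sunitinib liver dosing table (Table 11) has no combined transaminase-plus-bilirubin rule, so a potential Hy's Law case graded 2 or lower carries no required sunitinib hold

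*Protocol*

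**What the plan says.** The protocol gives each arm its own liver algorithm. Table 1, footnote 21 refers to the "hepatotoxicity algorithm (Section 6.8.1.2 for savolitinib and Section 6.8.2 for sunitinib)". Table 2, footnote 2 (Section 5.2.1) repeats the split: "Guidelines for management of hepatotoxicity are in section 6.8.1.2 for savolitinib and section 6.8.2 for sunitinib".

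- **Sunitinib.** Table 11 in Section 6.8.2 is titled "Dose modifications for sunitinib-related toxicities (including hepatic)". Grade 0, 1 or 2 has no action, and the first hold is at Grade 3. The hepatic paragraph of Section 6.8.2.1 uses the same threshold: "Sunitinib should be interrupted for Grade 3 or 4 drug-related hepatic adverse events and discontinued if there is no resolution".
- **Savolitinib.** Section 6.8.1.2 works from laboratory values. Its item 1 lists among the reasons to discontinue: "ALT or AST >3x ULN and (TBL>2x ULN or INR>1.5 if not on anticoagulants that elevate the INR)".
- **Hy's Law process.** Section 6.3.7 and Appendix E define a potential case as ALT or AST ≥3x ULN with total bilirubin ≥2x ULN, in either arm. Section 6.3.7 says: "Please refer to Section 6.8.1.2 and Appendix E for further instruction on cases of increases in liver biochemistry". The introduction to Appendix E likewise names only Section 6.8.1.2 for managing liver abnormalities. Neither mentions Section 6.8.2.

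**The concern.** A single-test grade does not capture the combination that defines potential Hy's Law. Each value can sit at a grade for which Table 11 prescribes nothing, while the pair is an event that Appendix E requires to be reported within 1 day as a related SAE. The site would then hold a dosing table saying no action is needed, and the Hy's Law pages would send it to the other drug's section, whose dose instructions name savolitinib only.

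Patient safety is at stake. Whether sunitinib is held in such a case depends on the judgement of the investigator and study physician, while on savolitinib it is a written rule. Section 6.8.2.1 itself warns that sunitinib hepatotoxicity can lead to liver failure or death. No efficacy estimate or test is affected.

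**Working it through.** The plan states no figure to reproduce, so the check sets the rules side by side.

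**Step 1. Transaminase grade.** Section 6.8.1.2, item 6 reads "Discontinue savolitinib for recurrent Grade 2 ALT or AST (>3-5x ULN)", so ALT/AST >3-5x ULN is Grade 2 in the protocol's own terms. Item 5 puts Grade 3 at >5x ULN. The potential Hy's Law threshold of ≥3x ULN is therefore reached within Grade 2.

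**Step 2. Bilirubin grade.** Section 6.3.3 says: "The grading scales found in the National Cancer Institute (NCI) CTCAE will be utilised for all events with an assigned CTCAE grading". The protocol prints no bilirubin cut-offs, so the upper end of Grade 2 has to be assumed:

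| Assumed upper limit of Grade 2 bilirubin | Cases with no required sunitinib hold |
|---|---|
| 3x ULN | ALT/AST >3-5x ULN with bilirubin from 2x to 3x ULN, event graded ≤2 |
| 2x ULN | Almost none |

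**Step 3. One patient under both algorithms.** Take ALT 4x ULN and bilirubin 2.5x ULN.

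| Rule | Result |
|---|---|
| Potential Hy's Law (Section 6.3.7, Appendix E) | Met: 4 ≥ 3 and 2.5 ≥ 2 |
| Savolitinib (Section 6.8.1.2, item 1) | Discontinue: 4 > 3 and 2.5 > 2 |
| Sunitinib (Table 11), bilirubin and event graded ≤2 | No action |
| Sunitinib (Section 6.8.2.1), same condition | Not triggered |
| Sunitinib (Table 11), bilirubin or event Grade 3 | Hold |

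**Step 4. Any other rule that requires a sunitinib hold.**

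- Appendix E asks for the SAE report, study-physician contact, monitoring and a search for the cause. It states no dose action. Even when the study drug is agreed to be the only explanation, the written step is an updated SAE.
- Section 6.8 allows temporary suspension, where judged appropriate, for situations its guidelines do not cover. That is discretionary. A site could also read Table 11 as already covering Grade 2 hepatic toxicity.
- Section 3.8 lists situations in which a patient may be discontinued, including by investigator decision. That is also discretionary.

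None of these requires a hold for the patient in Step 3.

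**Step 5. Size.** About 50 patients are randomised 1:1, so the sunitinib arm is 50 x 1/2 = 25 patients. One case would be 1/25 = 4% of the arm. The protocol gives no rate of potential Hy's Law on sunitinib, so no expected number of cases is calculated.

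**The case against.** The strongest case on the other side has four parts.

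1. **The width is unknown.** The gap needs both bilirubin and the event to be graded 2 or lower. If Grade 2 bilirubin ended at 2x ULN, almost nothing would remain. A potential Hy's Law event judged severe could also reach Grade 3 through the mild/moderate/severe conversion recommended in Section 6.3.3, which triggers the existing hold. Both points stand as limits. They do not close the gap, because Section 6.3.3 separates seriousness from severity, so an SAE report does not by itself make the event Grade 3.

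2. **Oversight is strong.** Section 1.5.1 provides an independent hepatic expert on the IDMC to evaluate potential Hy's Law cases, with liver safety reports supplied in real time. Section 5.2.1 routes such patients in either arm to Appendix E. Liver tests are weekly for the first nine tests in both arms. All of this stands: authority to hold and prompt review both exist. A stated dose action does not.

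3. **The arms differ for a reason.** Section 6.1.1 reports three Hy's Law cases on savolitinib, one with a fatal hepatic event. Sunitinib is an approved agent with its own hepatic text. This justifies a stricter savolitinib algorithm overall. It does not explain a table that prescribes no action for a combination the protocol treats as a related SAE in either arm. Section 6.8.2.1 already uses value-based sunitinib rules for ejection fraction and 24-hour urine protein, so a value-based liver row would not be foreign to it.

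4. **Few cases are likely.** The only sunitinib hepatic frequency in the protocol is liver failure in 7/2281 (0.3%, Section 6.8.2.1). Applied to 25 patients it gives 25 x 7/2281 ≈ 0.08. That is a liver-failure rate and not a potential Hy's Law rate, but it is fair context: the arm is small and there may be no case at all.

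**Conclusion.** The concern holds. For a sunitinib patient with ALT/AST >3-5x ULN and bilirubin ≥2x ULN, with bilirubin and the event graded 2 or lower, the protocol requires no hold and Table 11 prescribes no action. Essentially the same values require discontinuation of savolitinib. The defect is the absence of a required hold; nothing forbids one, and discretion and oversight are in place.

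The conclusion rests on Grade 2 bilirubin extending above 2x ULN, which the protocol neither confirms nor rules out. It concerns about 25 patients and possibly no cases. Part of the exposure was already past at version 6.0, although patients in screening could still be randomised and treatment has no maximum duration. Because the remedy is cheap and the event serious, it should be fixed. Confidence is medium.

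**What to change.** Add one row to Table 11: hold sunitinib, pending study-physician review, when ALT or AST is ≥3x ULN together with total bilirubin ≥2x ULN, whatever the grade of either test alone; discontinue sunitinib if no alternative cause is found. Because the row is written in multiples of ULN, it no longer depends on the unprinted bilirubin grades.

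Add Section 6.8.2 beside Section 6.8.1.2 in Section 6.3.7 and in the introduction to Appendix E, so that they agree with Table 1, footnote 21 and Table 2, footnote 2.

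This can be done by amendment or by a clarification letter to sites. The cost is an occasional extra sunitinib interruption. It needs no new assessments and no change to the analysis.
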